10.7 Telephone Interviews

The Study Coordinator will schedule a call with the subject within the visit window.

During the call, the subject is to be queried regarding the occurrence of any Adverse Events and Serious Adverse Events, per Section 12.0 Adverse Event Reporting. Any adverse event that results in reoperation or revision is to be recorded as a Serious Adverse Event.

The subject is to be queried regarding any reoperations of the index foot/ankle. All reoperations are to be documented using the Surgical Reoperation Form, per Section 11.1.

The subject will be reminded to complete the online surveys. The subject can also elect to complete the surveys via the telephone or mail. Any subject survey forms that are not collected via the database's ePRO system are to be maintained in the subjects' study files as source documents.

The Study Coordinator is to document the phone interview in the Telephone Log, including any completion of outcome measures via the phone.

At the 3, 4 and 5 year follow-up, the Study Coordinator will inquire about Adverse Events, Serious Adverse Events and reoperations, and remind the subject to complete the Global Satisfaction Survey and Numeric Pain Scale.

A Longitudinal Outcomes Study of the Subchondroplasty Procedure in the Foot/Ankle

Protocol #: KC.CR.I.AM.16.2 version 1

Table 1. Schedule of Events

	Visit 1	Visit 2	Visit 3	Post-Op Questionnaires	Post-Op Questionnaires	Post-Op Questionnaires	Post-Op Telephone Call
Procedures	Study Admit/ Pre- operative	Operative	SOC Post- Op Visit (7-21 days)	6 weeks	3 months 6 months	1 year 2 years	3 years 4 years 5 years
Visit Window	≤60 days Prior to Surgery			±7 Days	±14 Days	±60 Days	±60 Days
Informed Consent	X						
Inclusion & Exclusion Criteria	X						
Demographic Form	X						
Medical History	X						
Pain Medications/Therapies	X			P	P	P	
FFI	P			P	P	P	
Numeric Pain Scale	P		X	P	P	P	X
EQ-5D	P			P	P	P	
Global Satisfaction Survey				P	P	P	X
Surgical Documentation		X					
Adverse Event or Serious Adverse Event ²		(X)	(X)	(X)	(X)	(X)	(X)
Protocol Deviation ²		(X)	(X)	(X)	(X)	(X)	(X)
Telephone Contact ²				X	X	X	X
Surgical Reoperation ³			(X)	(X)	(X)	(X)	(X)
Study Exit ⁴		(X)	(X)	(X)	(X)	(X)	X

X Investigator completed forms

(X) Completed by Investigator when required

P Subject completed forms

² Case Report Forms to be completed if/when event occurs.

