³ Surgical Reoperation form will be completed if the investigator performs any procedure on the index foot/ankle regardless of whether the subject's change in condition is related to the initial study procedure.

⁴ Study Exit form will be completed if the subject is no longer participating in the study for any reason.

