11.0 Management of Intercurrent Events

11.1 Surgical Reoperation or Revision

A reoperation of the index foot/ankle or revision SCP injection site may be performed at the discretion of the Investigator (e.g., due to progressive pain or disability, etc.). A reoperation is defined as any surgical procedure on the index foot or ankle. For the purposes of this protocol, a revision will be defined as any partial or total joint arthroplasty or any fusion, bone fixation, bone grafting, or bone substitute procedure in the study foot or ankle.

The investigator is to dictate detailed operative notes that include the measures listed below, or have paper copies of the Surgical Reoperation Form completed during surgery to serve as a source document.

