11.1.1 Surgical Reoperation Documentation

- Reason for surgery

A Longitudinal Outcomes Study of the Subchondroplasty Procedure in the Foot/Ankle

Protocol #: KC.CR.I.AM.16.2 version 1

- Postoperative diagnosis
- OR Time
- Anesthesia Type
- Status of the Subchondroplasty Injection Location

If the reoperation occurs due to an adverse event, the event should be documented on a Serious Adverse Event Form and the surgery documented on the Surgical Reoperation Form.

11.1.2 In the event that a revision occurs (defined as any partial or total joint arthroplasty or any fusion, bone fixation, bone grafting, or bone substitute procedure in the index foot/ankle), the subject will be exited from the study. A Serious Adverse Event Form and Surgical Reoperation Form will be completed.

11.1.3 In the event that a reoperation occurs that does not involve revision of the BML site(s), a Serious Adverse Event Form and Surgical Reoperation Form will be completed, and the subject will continue to be followed in the study per protocol.

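### Sections 11.1.2 and 11.1.3 require a Serious Adverse Event Form for every revision and reoperation whatever the cause, while 10.7, 11.1.1 and 12.4 tie a serious event to an adverse event.

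*Combined protocol and SAP*

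**What the plan says.** Section 11.1 defines the term broadly: "A reoperation is defined as any surgical procedure on the index foot or ankle". Cause plays no part in that definition. A revision is a listed subset of such procedures (arthroplasty, fusion, fixation, grafting or bone substitute work).

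Two sub-sections ask for the SAE Form without any condition:

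- Section 11.1.2, for revisions: "A Serious Adverse Event Form and Surgical Reoperation Form will be completed".
- Section 11.1.3, for other reoperations: "In the event that a reoperation occurs that does not involve revision of the BML site(s), a Serious Adverse Event Form", to be filed along with the Surgical Reoperation Form.

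Four other places work from an adverse event, or leave the SAE Form out:

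- Section 11.1.1: "If the reoperation occurs due to an adverse event, the event should be documented on a Serious Adverse Event Form". The surgery itself goes on the Surgical Reoperation Form.
- Section 10.7: "Any adverse event that results in reoperation or revision is to be recorded as a Serious Adverse Event". For reoperations as such it says "All reoperations are to be documented using the Surgical Reoperation Form, per Section 11.1".
- Table 1 footnote 3: "Surgical Reoperation form will be completed if the investigator performs any procedure on the index foot/ankle", related or not. The SAE Form is not mentioned.
- Section 12.4 describes an SAE as an adverse event that meets one of four seriousness criteria. Section 12.0 defines an adverse event as something untoward that happens to the patient.

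**The concern.** The protocol gives two triggers for the same form. In one set of sections the trigger is the surgery. In the other it is an adverse event that led to the surgery. The two agree whenever an adverse event lies behind the operation. They part for an index-foot procedure with no such event, for example a planned removal of hardware placed in a concomitant procedure.

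What is at stake is the meaning of the safety counts. Section 13.0 has the sponsor review aggregated events for severity and incidence, and trends can lead to a protocol change or termination. Section 14.0 summarises complication data as frequencies and percentages. If SAE records include surgery with no adverse event, those counts no longer measure one thing. With up to 25 sites, handling could also differ from site to site.

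**Working it through.** The plan states no figure on this point, so the check is a comparison of the sections on one test case: a procedure on the index foot, not caused by any adverse event.

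| Section | Trigger for the SAE Form or SAE status | Result for the test case |
|---|---|---|
| 11.1.2 (if a revision) | the revision itself | SAE Form required |
| 11.1.3 (if not a revision) | the reoperation itself | SAE Form required |
| 11.1.1 | adverse event led to the reoperation | condition not met, no SAE Form |
| 10.7 | adverse event that results in surgery | nothing to record as an SAE; Surgical Reoperation Form only |
| Table 1 footnote 3 | none named | Surgical Reoperation Form only |
| 12.4 | adverse event plus a seriousness criterion | not an SAE |

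Three steps follow.

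1. Sections 11.1.2 and 11.1.3 together cover both revisions and other reoperations. If both are obeyed, every reoperation gets an SAE Form and the condition in 11.1.1 has no work to do.
2. The form then asks for what cannot be given. Section 12.4 has the investigator judge how the adverse event relates to the procedure and device, and in the test case there is no adverse event to judge.
3. The resulting record sits among the SAE records but fails the 12.4 definition.

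The size cannot be derived: the documents give no rate for SAEs, reoperations or planned surgery. As illustration only, assume that a share s of subjects has a genuine SAE over 5 years, that a share e has an index-foot procedure with no adverse event behind it, that the two are independent, and that every such form is counted as an SAE.

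- Extra subjects counted = 250 × e × (1 − s).
- With s = 0.10 and e = 0.04: 250 × 0.04 × 0.90 = 9.0.
- With s = 0.05 and e = 0.10: 250 × 0.10 × 0.95 = 23.75, about 24.

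Both ranges (s from 5% to 10%, e from 4% to 10%) are assumptions. If e is close to zero, so is the effect. The inconsistency does not depend on these figures.

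**The case against.** The best defence is that the rules are compatible. Neither 11.1.1 nor 10.7 contains the word only. Each can be read as a sufficient condition, so a site that always files the SAE Form breaches nothing, and the matching wording of 11.1.2 and 11.1.3 may be deliberate over-capture of safety data. It is true that an exclusive reading of 11.1.1 and 10.7 is an inference. But the permissive reading leaves the condition in 11.1.1 without effect, and it does not resolve the mismatch with 12.4.

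Other points for the defence stand and limit the claim:

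- Filing a form is not a finding of relatedness. Section 12.1 includes a rating of no relationship, and 12.0 restricts sponsor reporting to possibly or definitely related events. A reader might infer that planned surgery becomes a serious complication of the product; the text does not go that far.
- Section 14.0 speaks of complication data. It names no serious-event percentage, threshold or test.
- The affected group may be small. The examples of reasons for reoperation in 11.1 are progressive pain and disability. Worsening of an existing condition meets the 12.0 definition, and a need for surgery meets 12.4, so the rules agree there.
- A reader might take the two ankle cases in Section 5.4 as evidence that staged surgery is to be expected. They had concomitant procedures; no planned second operation is described.
- The case report forms in Appendix C are not in the text available for review, so whether the SAE Form already separates such cases is unknown.
- The reason for surgery and postoperative diagnosis are already collected, so an analyst could separate the cases. The plan does not say that this will be done.

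**Conclusion.** The inconsistency is real and rests on the text alone. Sections 11.1.2 and 11.1.3 generate SAE records for index-foot surgery with no adverse event behind it, and such records do not meet 12.4. Event counts under 13.0 and complication frequencies under 14.0 could therefore mix adverse events with surgery that had none.

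The size is unknown. The 9 to 24 subjects above show scale under assumed rates and are not an estimate. Nor do the documents show that sites will in fact apply different rules, since 11.1.2 and 11.1.3 are explicit; the risk arises because other sections point elsewhere. This is a data-definition defect in a descriptive study. It is worth correcting and does not threaten the design.

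**What to change.** Reconcile 10.7, 11.1.1, 11.1.2, 11.1.3 and 12.4 to one stated trigger for the SAE Form. Changing 11.1.3 alone would leave the same problem for revisions. Then:

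- Keep the Surgical Reoperation Form for every reoperation, as 10.7 and Table 1 footnote 3 already require.
- Use its existing reason-for-surgery item to class each procedure as due to an adverse event or as planned/other.
- In 14.0, report the all-reoperation rate, the revision rate and the SAE rate on separate lines, and count in the SAE line only events that meet 12.4.

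If the sponsor wants the SAE Form for all reoperations as deliberate over-capture, the protocol should say so, drop the condition in 11.1.1, and flag procedures with no adverse event so that they are left out of the SAE rate.

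Either route costs a few sentences and one classification, largely from data already collected. The downside is that sites must judge whether an adverse event led to the surgery. The all-reoperation line guards against under-calling, because no reoperation drops out of the report.

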11.2 Postoperative Injections

Use of any postoperative injections into the index foot/ankle should be recorded on the Medication Form at the next questionnaire completion window.

11.3 Missed Follow-up Completion of Questionnaires

If a subject fails to complete the post-operative questionnaires at a follow-up time point, the site should continue to attempt follow-up of the subject through the five year study end point. The subject should only be exited from the study under the conditions described in section 11.7.

11.4 Protocol Amendments

Any proposed amendments to this protocol must be submitted in writing and pre-approved by the Sponsor. All Sponsor-initiated protocol amendments will be documented in writing, including the date and justification for the change, and communicated in a timely manner to the investigators. All amendments are to be approved by the reviewing IRB prior to implementation.

11.5 Unscheduled Office Visits

Investigators may see the subjects, at their professional discretion, outside of the time points described in the study protocol. If an adverse event (AE) is reported during an unscheduled visit, the AE should be documented per Section 12.0 Adverse Event Reporting. No additional data collection or Case Report Forms are required at the unscheduled visit.

11.6 Protocol Deviations and Violations

The Investigator(s) agrees to conduct the study in accordance with this protocol. For the purpose of this study, **only** violations that affect the subject's rights, safety, or welfare, or the integrity of the data will be recorded.

11.6.1 A protocol violation can be described as accidental or unintentional change to, or non-compliance with the IRB approved protocol without prior Sponsor and IRB approval. Violations generally increase risk and/or decrease benefit, affects the subject's rights, safety, or welfare, or the integrity of the data. Examples include failure to obtain valid informed consent (e.g., obtained informed consent on an unapproved consent form), loss of laptop/computer that contained identifiable and private information about subjects or not following inclusion/exclusion criteria.

Any deviations to inclusion or exclusion criteria must be submitted to Zimmer Biomet and the reviewing IRB, where applicable, for analysis and approval prior to subject enrollment.

All protocol violations shall be reported to Zimmer Biomet within 24 hours and to the reviewing IRB per policy. A Protocol Violation Form shall be completed that includes a full explanation of the event and outcome.

The Investigator will assist Zimmer Biomet in corresponding with the reviewing IRB, where appropriate, to determine the appropriate course of action.

11.6.2 Protocol deviations will **not** be collected for this study. A protocol deviation is an accidental or unintentional change to or non-compliance with the research protocol that does not increase risk or decrease benefit or does not have a significant effect on the subject's rights, safety or welfare, and/or on the integrity of the data. A deviation may be due to the research subject's non-adherence or an unintentional change to or non-compliance with the research protocol on the part of a researcher.

11.7 Withdrawal and Study Re-Entry

During the course of the study, it is possible that subjects will be withdrawn from the study. Factors leading to subject withdrawal may include, but are not limited to, the following:

Subject Withdrawal – A subject may voluntarily withdraw from the study at any time without prejudice or affecting their future medical treatment. Investigators may withdraw a subject due to non-compliance with the protocol or follow-up questionnaire schedule, or for any other reason per their professional opinion. The date and reason for subject withdrawal is to be documented on the **Study Exit** form.

If a subject is withdrawn or terminated due to medical safety considerations because of an adverse event, the adverse event must be followed by the investigator to satisfactory resolution or until the investigator determines the event to be chronic or clinically stable. All study data related to event is to be recorded.

Subject Lost to Follow-Up – If the subject does not complete the required questionnaires and the Investigator or Study Coordinator has attempted to contact that subject at least three times via telephone and receives no response, the subject may be deemed to be lost to follow-up. The research staff will document the attempts to contact the subject. The final attempt to contact the subject will be performed by register/return receipt mail. The receipt will be placed in the

subject's binder. A study Exit Form must be completed.

Should a subject who previously chose to withdraw or was considered lost-to-follow-up wishes to re-enter the study, a new Informed Consent will be required. The site may resume scheduled follow-up visits from the subject's last follow-up visit.

Subject Death – Should a subject expire, complete the Adverse Event and Study Exit Form. Submit copies of the death certificate, autopsy report (if applicable and available) and source documents related to the death. The Investigator will make written notification to the IRB upon the death of a subject in the study.

When a subject withdraws or is withdrawn, all study procedures completed and data collected prior to the date of withdrawal will be submitted to the sponsor and included in the study database, unless the subject requests otherwise in writing.

12.0 Adverse Event Reporting

An **adverse event (AE)** is defined as an untoward medical occurrence, unintended disease or injury, or untoward clinical signs (or change or worsening of a pre-existing medical condition) in a patient, which may or may not have an association with the device. In addition an adverse device effect is defined as 'any untoward and unintended response to a medical device'.

For this study, **only AEs which are possibly or definitely related to the device or procedure will be reported to the sponsor**. The determination whether the AE is related to the device or procedure will be based upon whether a causal relationship between the device or procedure and the AE is at least a reasonable possibility, i.e., the relationship cannot be ruled out. A causal relationship cannot be ruled out if, in the medical judgment of the investigator, the effect follows a reasonable temporal association with the use of the device. See Section 12.1.

In the event there is an exacerbation of the pre-existing medical condition or symptoms (due to the device or study related procedure), then an AE must be reported.

12.1 Relationship to study device or procedure

The relationship to the study device or procedure should be rated as follows:

- **None** (definitely not related): there is no relationship between study device or procedure and the event.
- **Possible** (remote possibility, possibly, or probably related): the relationship between study device or procedure could exist if there is no contradicting evidence that can reasonably explain the Subject's condition.
- **Definite** (definitely related): the relationship between study device or procedure and event does exist and is confirmed upon further investigation by the investigator.

- Subjects should be encouraged to report AEs spontaneously and may volunteer AE information at any time. At each evaluation, the investigator will determine whether an AE has occurred. If it is determined that an AE has occurred, the investigator should obtain all the information required to complete the appropriate AE form(s). If an event occurs at an outside institution, the investigator should attempt to obtain, if possible, required AE information to report to the Sponsor.

12.2 Adverse Event Data Collection

The Adverse Event Form will collect the following:

- Description of complication
- Date of onset
- Severity/Intensity of symptoms
 - Mild: Event/symptom is transient and well tolerated by the subject.
 - Moderate: Event/symptom causes discomfort and interferes with routine activities of the subject.
 - Severe: Event/symptom interferes considerably with the routine activities of the subject or causes inability to work.
- Duration
- Relationship to surgical procedure
- Relationship to product
- Treatment
- AE Outcome

12.3 Events Followed to Resolution

Any Adverse Event considered by the Investigator to be possibly or definitely related to the Subchondroplasty procedure should be followed over the study period until resolution or until the Investigator determines the event is chronic or clinically stable.

12.4 Serious Adverse Events

A Serious Adverse Event (SAE) is described as any adverse event that is:

- Fatal;
- Life-threatening*;
- Results in permanent impairment of a body function or permanent damage to body structure; or
- Necessitates medical or surgical intervention, including hospitalization

** NOTE: the term “life-threatening” refers to an event in which the subject was at a risk of death at the time of the event; it does not refer to an event which hypothetically might have caused death if it were more severe.*

If an AE is determined to be serious (i.e., an SAE), the Investigator(s) will determine the

relationship of the adverse event to the procedure, device, or any commercial products used during the period of the study and complete a **Serious Adverse Event Form**. Death is considered to be an outcome of an Adverse Event and documented on the Serious Adverse Event Form. The actual cause of death (rather than the term “death”) should be recorded on the form. All SAEs will be followed until resolution or the Investigator judges the event to be chronic or stable.

The Investigator must report all SAEs that meet the criteria below to a Zimmer Biomet Study Representative within twenty-four (24) hours after becoming aware of the incident:

- Definitely or possibly related to the Study Procedure AND unexpected

The Investigator is responsible for notifying the IRB of all Adverse Events, including SAEs, in accordance with local regulations and institutional policies.

If an Unanticipated Serious Adverse Device Effect (USADE) is identified by the Sponsor, it will be promptly reported to concerned Investigators and regulatory authorities as required by applicable regulatory requirements. If applicable per their reporting requirements, the Investigator or Designee will report the USADE to their IRB or EC.

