6.1 Risks of surgical intervention

With any surgical procedure, there are risks of complication including those risks currently associated with surgical interventions in the foot/ankle. These risks include intra-articular adhesions (scar tissue), superficial and/or deep wound infection, nausea and/or vomiting, bleeding, ankle pain, muscle weakness, and postoperative blood clot (hematoma). There are possibilities of wound re-opening, deep vein thrombosis (blood clot), pulmonary embolus (lung clot), vascular or nerve injury, and an allergic response to the anesthetic or medications. Some additional risks related to local anesthesia are swelling, pain, bleeding, bruising, nerve pain and loss of sensation in the skin and ligament around the foot/ankle.

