13.0 Assessment of Safety

All reports of Adverse Events will be entered into the study database and evaluated by the Sponsor or their designee on a regular basis throughout the study. These reports will be made available to the Investigator for preparation of IRB continuing review reports, when requested.

Individual and aggregated events will be reviewed for consistency with expected events, for both severity and rate of incidence. Individual events or trends in events that appear to impact subject safety are reviewed by Zimmer Biomet management to determine if a change in the protocol or termination of the study is warranted. These decisions will be promptly communicated to all Investigators and local IRBs.

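### The fourth seriousness criterion in Section 12.4 has no qualifier, so a related event needing any medical treatment is an SAE as written, and SAE counts become hard to interpret

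*Combined protocol and SAP*

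**What the plan says.** Section 12.4 lists four criteria for an SAE. The first two are a fatal event and a life-threatening event. The third is "Results in permanent impairment of a body function or permanent damage to body structure; or", and its closing conjunction leads to the fourth: "Necessitates medical or surgical intervention, including hospitalization". A note in the same section narrows the term life-threatening. Nothing narrows the fourth criterion.

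Severity is a separate scale. Section 12.2 grades events Mild, Moderate or Severe on the Adverse Event Form, the lowest grade being "Mild: Event/symptom is transient and well tolerated by the subject". The same list of form fields includes treatment and outcome.

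Two filters act on what the sponsor receives. Under Section 12.0, "only AEs which are possibly or definitely related to the device or procedure will be reported to the sponsor". Under Section 12.4, the 24-hour duty covers SAEs that are "Definitely or possibly related to the Study Procedure AND unexpected".

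Section 10.7 adds a rule on surgery: "Any adverse event that results in reoperation or revision is to be recorded as a Serious Adverse Event". Section 11.1 has further rules on the same subject. On use of the data, Section 14.0 summarises complications as counts and percentages, and Section 13.0 says: "Individual and aggregated events will be reviewed for consistency with expected events, for both severity and rate of incidence".

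**The concern.** The first three criteria concern death, threat to life and permanent harm. The fourth sets no comparable threshold. The words on hospitalisation give an example of an intervention; they do not set a minimum. The surgical half of the criterion gets some content from the reoperation rules, but the medical half gets none.

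The risks in Section 6.1 include "superficial and/or deep wound infection, nausea and/or vomiting, bleeding, ankle pain". Several of these can be handled with a drug or a dressing. If sites apply the words literally, such events become SAEs. If some sites apply a narrower reading, the same event is classified differently from site to site, and the protocol allows up to 25 sites. The classification decides which form is completed, is one condition of the 24-hour report, and determines any SAE percentage that appears in a report or publication.

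**Working it through.** The documents state no SAE rate, safety threshold or sample-size derivation, so there is no figure to reproduce. The check is mainly of the text.

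**1. Does the fourth criterion stand alone?** Yes. The criteria are alternatives, and the intervention criterion is not tied to the permanent-impairment criterion before it.

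**2. Test case: a superficial wound infection needing oral antibiotics.**
- Related? Section 12.0 counts an event as related if a relationship cannot be ruled out, and the Possible category in Section 12.1 extends down to a remote possibility. A postoperative wound infection would generally pass.
- Serious? It needs a medical intervention, so the fourth criterion is met.
- Severity? It may be graded Mild or Moderate under Section 12.2.
- Result: an SAE of mild or moderate severity, recorded on the Serious Adverse Event Form.

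**3. Comparison with the ordinary form.** The treatment field in Section 12.2 implies that some non-serious events are treated. Under Section 12.4, an event that needs treatment is serious. The two fit together only for treatment that was given but not needed.

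**4. The reoperation rules side by side.**
- Section 10.7: an adverse event that leads to reoperation or revision is an SAE.
- Section 11.1.1: a Serious Adverse Event Form is used if the reoperation is due to an adverse event.
- Section 11.1.2: any revision requires a Serious Adverse Event Form.
- Section 11.1.3: a reoperation that does not revise the treated site requires a Serious Adverse Event Form, with no condition that an adverse event caused it.

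The first two depend on an adverse event; the last two do not.

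**5. Illustration of size.** All rates here are assumptions; only n = 250 (target enrolment, Section 8.0) comes from the protocol. Let s be subjects with an event serious under a narrower definition, and m be further subjects with only a minor, related, treated event.

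SAE proportion as written = (s + m)/n; minor share = m/(s + m).

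With s = 5, the narrow proportion is 5/250 = 2.0% (exact 95% CI 0.7% to 4.6%).
- m = 13 (5% of 250 is 12.5): 18/250 = 7.2%; minor share 13/18 = 72%.
- m = 50 (20% of 250): 55/250 = 22.0%; minor share 50/55 = 91%.

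With other assumed values of m:

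| m | s = 5 (2.0%) | minor share | s = 12 (4.8%) | minor share |
|---|---|---|---|---|
| 5 | 4.0% | 50% | 6.8% | 29% |
| 12 | 6.8% | 71% | 9.6% | 50% |
| 25 | 12.0% | 83% | 14.8% | 68% |
| 38 | 17.2% | 88% | 20.0% | 76% |

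If only a fraction f of the minor events is classified literally, the proportion is (s + f·m)/n. With s = 5 and m = 50, f = 0, 0.5 and 1 give 2%, 12% and 22%. The same events therefore yield different percentages according to how sites read one sentence.

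**The case against.** The strongest reply concerns impact. The plan is descriptive and names no SAE rate, endpoint, comparison or threshold. Section 13.0 works from severity, incidence and individual events, and the seriousness label changes none of these. The 24-hour duty requires an event to be unexpected; minor complications listed in Section 6.1 would presumably be expected and so would not flood expedited reporting. All of this stands.

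A reader might therefore infer too much: that the serious-event rate loses its meaning, or that grave events such as embolism or deep infection are diluted and missed. The documents do not support either. No serious-event rate is specified, and because events are reviewed individually a grave event can still be seen by its description.

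The reply also notes that the criterion says an event must necessitate intervention, so an optional antiemetic or analgesic for a well-tolerated symptom need not qualify. That is fair, and it weakens the nausea and pain examples. It does not help with an infection that needs antibiotics. The treatment field in Section 12.2 may show that treated non-serious events were intended, but the definition does not say so.

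Variation between sites is an inference. Sponsor staff review and query submitted forms (Section 15.2), and the case report forms in Appendix C are not in the text reviewed, so a narrower instruction there cannot be excluded. If one exists, Section 12.4 should match it. Finally, over-capture is the cautious direction for safety. That argues against alarm, but it does not justify leaving the definition unclear.

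**Conclusion.** The defect is real and limited. As written, a related event of any severity grade that needs any medical treatment is an SAE. This conflicts with the ordinary form in Section 12.2 and makes any SAE count or percentage hard to interpret or to compare across sites. It does not undermine a planned analysis or decision rule, because none rests on SAE counts.

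Its size cannot be derived from the documents. The rise from 2% to about 7% to 22% assumes the underlying rates, assumes that minor events fall in subjects other than the first five, and assumes that every site reads the criterion literally. It shows that the inflation could be material, not that it will be. The change should be made because it is cheap and because seriousness governs form choice and eligibility for 24-hour reporting.

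**What to change.** Amend the fourth criterion in Section 12.4 to cover hospitalisation, and medical or surgical intervention needed to prevent death, a life-threatening condition, or permanent impairment or damage. State that other treated related events go on the Adverse Event Form.

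Reconcile the criterion with Sections 10.7, 11.1.1, 11.1.2 and 11.1.3, so that one rule says when a reoperation or revision is an SAE and when the Serious Adverse Event Form is used for documentation only.

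Apply the new wording prospectively. For events already entered, keep the classification as recorded and note which criterion was met. Do not relabel them: that would lower the SAE count after the data have been seen, in a study run by the sponsor. Add to Section 14.0 a table of subjects with at least one SAE, by criterion, severity and type of intervention, under both definitions. This requires severity and treatment to be available for SAEs too; Section 12.2 lists those fields only for the Adverse Event Form.

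The cost is a short amendment, a memo to sites, and a check of the criterion met for entered events. The downside is a lower SAE count and fewer events eligible for 24-hour reporting, namely related, unexpected, treated events that meet no other criterion. Those events are still captured as adverse events.
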